The proposed study will employ a between subjects prospective design to follow 168 Veterans with CUD and co-occurring insomnia over the course of six months while individuals complete a treatment/placebo group within the context of outpatient addiction treatment at the Menlo Park division of the VA Palo Alto Health Care System. Overall, this design will involve assessments during the following times: baseline (prior to the intervention), over the course of the intervention, upon completion of the treatment/placebo group conducted during week 6 (completion of the sleep [or placebo] intervention), and three follow-up assessments conducted 2-weeks, 4-weeks, and 6-months post-treatment. Veterans will be recruited through the outpatient substance abuse treatment program within the Menlo Park Division of the VA Palo Alto Health Care System and through fliers placed throughout the community. Interested participants will complete a brief phone-based screening with a trained research assistant to assess for initial inclusionary/exclusionary criteria. Eligible individuals will then be scheduled for a baseline assessment once enough individuals have been recruited to comprise three groups for the treatment/placebo group portion. Baseline assessments will consist of structured clinical interviews, questionnaires, and a urine toxicology to assess for the presence/absence of marijuana. Eligible participants will then be randomly assigned to one of three conditions: (1) CBT-I with adjunctive sleep mobile app (CBT-I-MA); (2) CBT-I only (CBT-I); or (3) Placebo-control(PC). The treatment/placebo groups will occur weekly for six consecutive weeks. During this time, substance use (including

Title: The Impact of CBT-I on Cannabis Cessation Outcomes
Approval Period: 03/27/2015 - 03/11/2016

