e) Describe alternative procedures or courses of treatment, if any, that might be advantageous to the participant. Describe potential risks and benefits associated with these. Any standard treatment that is being withheld must be disclosed in the consent process and form. (i.e. standard-of-care drug, different interventional procedure, no procedure or treatment, palliative care, other research studies).

The alternative is not to participate in the study. As there is no formal intervention component to the current study, there is no alternative treatment course for those who do, versus those who do not, participate in the study. All participants will have access to substance use treatment within VA, consistent with treatment guidelines.

f) Will it be possible to continue the more (most) appropriate therapy for the participant(s) after the conclusion of the study?

The outpatient SUD treatment program is currently available at the VA Palo Alto. Thus, patients can utilize it at any time. The VAPAHCS also offers cognitive behavioral therapy for insomnia which can be accessed by veterans.

g) Study Endpoint. What are the guidelines or end points by which you can evaluate the different treatments (i.e. study drug, device, procedure) during the study? If one proves to be clearly more effective than another (or others) during the course of a study, will the study be terminated before the projected total participant population has been enrolled? When will the study end if no important differences are detected?

Title: The Impact of CBT-I on Cannabis Cessation Outcomes
Approval Period: 03/27/2015 - 03/11/2016

N/A.

3. Background

a) Describe past experimental and/or clinical findings leading to the formulation of the study.

The Prevalence of cannabis use disorder (CUD) has been steadily increasing within the Veteran Health Administration (VHA), along with the related significant physical, cognitive, and psychological sequelae. Even in patients with a strong motivation to quit and the presence of empirically-supported interventions (Roffman & Stephens, 2006), Veterans who receive treatment for CUD have high rates of lapse (63% by 6-months post-treatment) and relapse (71% within 6-months post-treatment; Moore et al., 2003). Thus, identifying strategies to improve response to CUD treatment is in the interest of all VHA stakeholders.

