- f) State the number, if any, of participants who are healthy volunteers. Provide rationale for the inclusion of healthy volunteers in this study. Specify any risks to which participants may possibly be exposed. Specify the measures being taken to minimize the risks and the chance of harm to the volunteers and the additional safeguards that have been included in the protocol to protect their rights and welfare.**

No healthy volunteers will be involved. All subjects will have a substance use disorder.

- g) How will you identify participants for recruitment? (E.g., by: chart review; referral from treating physician; response to ad). Attach recruitment materials in Section #16 (Attachments). All Final or revised recruitment materials, flyers, etc. must be submitted to the IRB for review and approval before use. You may not contact potential participants prior to IRB approval. See Advertisements: Appropriate Language for Recruitment Material.**

We will implement a multi-pronged recruitment process.

(1) We will advertise the study to each Veteran presenting to the outpatient SUD treatment center at VAPAHCS. In addition, staff within the outpatient SUD treatment center will provide study and contact information to patients beginning the program. In order to ensure enrollment of individuals with comorbid insomnia, we will also advertise within the outpatient SUD treatment center with flyers that specifically mention insomnia symptoms.

(2) We will recruit through flyers and presentations throughout the VAPAHCS including community based outpatient clinics.

(3) We will recruit (through flyers and presentations) in community locations where veterans congregate (this may include but is not limited to VFW's and local colleges with veterans programs).

(4) Advertisements will be placed in local newspapers. TV and radio advertisements will be placed.

(5) Recruitment through social media will be used including but not limited to recruitment through Facebook ads, Twitter, and Craigslist.

(6) We will recruit through veterans programs within local colleges and universities including San Jose

Title: The Impact of CBT-I on Cannabis Cessation Outcomes
Approval Period: 03/27/2015 - 03/11/2016

State University (point of contact San Jose State University: [name] and [name]).

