(7) We will provide staff within veterans programs forms which they will distribute to individuals within their program. The forms will inquire if individuals are interested in hearing more about potential options for participating in research. They will be asked to check yes or no regarding their interest and provide their name and contact information. Study staff will collect the forms from the staff once/week and will contact those individuals indicating they were interested in research participation. This form can be found in section 16.

Patients interested in the study will contact the research laboratory to complete a brief phone screening for initial eligibility criteria and schedule a baseline appointment.

h) Inclusion and Exclusion Criteria.

Identify inclusion criteria.

To be included in the current study individuals must (1) be a Veteran 18 years or older; (2) meet DSM-5 diagnostic criteria for cannabis use disorder; and (3) meet DSM-5 diagnostic criteria for insomnia.

Identify exclusion criteria.

Individuals will be excluded based on evidence of the following: (1) inability to provide fully-informed written consent to participate; (2) history of, or current, psychotic symptoms or bipolar disorder; (3) current pregnancy; (4) sleep apnea as indicated by a score ≥ 5 on the STOP-Bang assessment; and (5) active suicidal/homicidal intent.

i) Describe your screening procedures, including how qualifying laboratory values will be obtained. If you are collecting personal health information prior to enrollment (e.g., telephone screening), please request a waiver of authorization for recruitment (in section 15).

Participants calling the laboratory with interest in the study will be briefly screened over the telephone to determine if they are likely to be study eligible. Likely eligible participants will be enrolled in the study and assessed for presence of cannabis use disorder, using the structured clinical interview for DSM-5, and insomnia (using the insomnia severity index). Participants who are positive for cannabis use disorder and insomnia, will be included in the study. Participants who are negative for cannabis use disorder or insomnia, will end study participation at this point.

j) Describe how you will be cognizant of other protocols in which participants might be enrolled. Please explain if participants will be enrolled in more than one study.

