The proposed study will take place in the context of outpatient substance abuse treatment within VA Palo Alto's Outpatient Addiction Consultation and Treatment Program (see letter of support from [name]). This program is comprised of outpatient group-based substance abuse treatment. Treatment consists of five hours of group-based substance-focused therapy per week. In addition, 75% of Veterans enrolled in this program receive three hours of therapy per week focused on comorbid psychiatric conditions; however treatment for insomnia is not provided. In FY 2011, 485 unique patients were treated through the outpatient treatment program for a CUD. The majority of individuals were self-referred to this program (75%), with a minority of individuals being legally mandated to treatment (2%). Upon admission to the program individuals are screened for co-occurring symptoms, however, they are not required to complete detoxification. The outpatient program provides treatment for a broad range of substance use disorders, including CUD. The treatment components include: psychoeducation, motivational enhancement, cognitive behavioral therapy for relapse prevention, and supportive group therapy. In conjunction with this treatment protocol, approximately 90% of individuals participate in 12-step groups such as Alcoholics Anonymous. Treatment is administered by members of the 15 person full-time staff, including two clinical psychologists. Importantly, individuals engage in components of treatment outlined above prior to their quit attempt. Within this context, a formal quit day is not determined. In the current study, this existing treatment will be augmented by including a treatment/placebo group prior to the cessation attempt and will formalize a set quit day which will occur after completion of the treatment/placebo group (see below for group details). This design will not result in a delay of VA treatment.

Treatment Administered:

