Inclusion and exclusionary criteria was carefully considered in order to balance internal and external validity with minimal risk and greatest benefit to participants. To be included in the current study individuals must (1) be a Veteran 18 years or older scheduled to begin outpatient SUD treatment at VAPAHCS; (2) meet DSM-5 diagnostic criteria for cannabis use disorder; (3) meet DSM-5 diagnostic criteria for insomnia; (4) endorse a motivation to quit, evidenced by actively thinking about/or having a plan to quit in the next month; and (5) be willing to formalize and agree to a quit day which will occur after completion of the treatment/placebo group. Individuals will be excluded based on evidence of the following: (1) inability to provide fully-informed written consent to participate; (2) history of, or current, psychotic symptoms; (3) current pregnancy; (4) apnea hypopnea index (AHI) >15, indicative of moderate to severe sleep apnea; and (5) active suicidal/homicidal intent. Suicidal and homicidal intent will be assessed in the context of a structured clinical interview (see section 2a.3., “measures” subsection for details). In the case that respondents endorse active intent they will be referred immediately for treatment and will be excluded from the current study.

2a.3.f. Participant Retention.

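### The protocol no longer ties entry to the outpatient SUD programme and recruits from the community, but programme treatment is neither scheduled for recording nor in the stated models

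*Protocol*

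**What the plan says.** **Eligibility.** SAP section 2a.3.e requires each participant to "be a Veteran 18 years or older scheduled to begin outpatient SUD treatment at VAPAHCS", and SAP section 2a.3.c confines recruitment to that programme. Protocol section 8h has no such condition: "individuals must (1) be a Veteran 18 years or older; (2) meet DSM-5 diagnostic criteria for cannabis use disorder", with DSM-5 insomnia as the third criterion.

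**Recruitment.** Protocol section 2a adds recruitment "through fliers placed throughout the community". Section 8g goes further: "We will recruit (through flyers and presentations) in community locations where veterans congregate", and "Advertisements will be placed in local newspapers. TV and radio advertisements will be placed". Social media and college veterans' programmes are also listed.

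**Setting.** Protocol section 2a still places the groups "within the context of outpatient addiction treatment at the Menlo Park division", and section 8c argues for a sample representative of outpatient SUD patients. Section 2e gives all participants access to VA substance use treatment but does not require them to receive it.

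**Background care.** SAP section 2a.3.b describes the programme: "Treatment consists of five hours of group-based substance-focused therapy per week". Of those enrolled, 75% receive a further 3 h/week for comorbid psychiatric conditions. Study therapy is six one-hour sessions (Protocol section 8m).

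**Measurement and analysis.** SAP Table 1 has no row for SUD or other psychosocial treatment. Its only concomitant-treatment measure, the PMI, covers medication. The H1.1 and H2.1 models (SAP section 2a.3.j) contain group, baseline value and a random person effect, and H1.2 names no covariate. No stratification factor is given. Listed confounders are examined as exploratory moderators if arms differ, and background treatment is not on the list.

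**The concern.** Under the SAP's entry rule, programme treatment was a common background and the trial tested CBT-I added to it. Under the protocol's entry rule that background can differ between participants, and it is aimed directly at the Aim 1 outcomes: the programme includes motivational enhancement and CBT for relapse prevention.

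The SAP records medication at every assessment so that its role can be examined. The same reasoning applies to therapy that targets cannabis use.

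Without a record of programme status, the analysis cannot adjust for a plausible prognostic factor. It also cannot show whether arms differ in care taken up after randomisation, or say whether a result applies to CBT-I given alongside SUD treatment, which is the use described in Protocol sections 1b and 3a.

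**Working it through.** The plan gives no figure for this point, so there is nothing to reproduce. The check sets out the contrast in hours and then illustrates the statistical cost.

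**1. Hours**
- Programme (SAP 2a.3.b): 5 h/week, or 5 + 3 = 8 h/week for the 75% with psychiatric therapy. The mean is 5 + 0.75 × 3 = 7.25 h/week.
- Study (Protocol 8m): 1 h/week.
- Over six weeks: 6 × 5 = 30 h or 6 × 8 = 48 h, against 6 × 1 = 6 h. This assumes full attendance and complete overlap with the six group weeks, neither of which is stated.
- Someone recruited from the community may have 0 h. The criteria permit this, but no passage states it.

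**2. Lost precision if programme status is left out**
- Assumptions (the documents give neither): share p in the programme, 25-75%; outcome difference δ between those in and out, 0.25-0.8 within-stratum SD.
- Variance factor: 1 + p(1 − p)δ².
- Smallest: 1 + 0.25 × 0.75 × 0.25² = 1.012. Largest: 1 + 0.5 × 0.5 × 0.8² = 1.16.
- Reading the SAP's d = .42 on the within-stratum scale, it shrinks to .42/√1.012 = 0.418 at best and .42/√1.16 = 0.390 at worst.
- Normal-approximation power, two-sided alpha .05, for the two CBT-I arms combined against placebo (112 v 56) is 0.728 at d = .42. It falls to 0.723 (0.5 points lost) or 0.664 (6.4 points lost).
- At a more extreme δ = 1.0 SD with p = 0.5, the factor is 1.25, d is 0.376 and power is 0.631 (9.7 points lost).

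**3. Chance imbalance between two arms of 56**
- SE of the difference in programme share: √(2p(1 − p)/56). This is 0.082 at p = 0.25 or 0.75 and 0.094 at p = 0.5.
- Imbalance exceeded in 5% of randomisations: 1.96 × SE = 0.160 to 0.185.
- Shift in the unadjusted contrast (imbalance × δ): 0.160 × 0.25 = 0.04 SD at the low end, and 0.185 × 0.8 = 0.15 SD at the top of the range in step 2. With δ = 1.0 it is about 0.19 SD.

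**4. Text side by side**
- Protocol 8g and 8h admit community recruits with no programme requirement. Protocol 2a and 8c describe a programme sample. Both are in the current protocol, so the inconsistency does not depend on comparing it with the older SAP.

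**The case against.** **Randomisation already handles this.** Largely correct. A reader might take the 0.04-0.19 SD shift as bias. It is not: baseline programme status is balanced in expectation, the ordinary standard error of the unadjusted contrast covers chance imbalance, and type I error is unaffected. The values of δ are assumptions. H1.1 already adjusts for baseline use, which would absorb some of the effect, and the SAP's hypothesised Aim 1 effect is d = 1.4, far larger than these shifts.

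**No passage says that untreated participants will be enrolled.** Also correct. A reader might infer that the site will randomise people with no SUD care against others with 8 h/week of cannabis-relevant therapy. The criteria allow the former but do not state it, and all participants have access to VA treatment. Three of the 8 hours are for psychiatric conditions, and the other five serve a broad range of substance use disorders.

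**Contamination by CBT-I outside the study.** A reader might infer from "The VAPAHCS also offers cognitive behavioral therapy for insomnia which can be accessed by veterans" that placebo participants will readily obtain CBT-I. That sentence (Protocol 2f) answers a question about therapy after the study ends, and Protocol 3a says that Veterans with SUDs rarely receive CBT-I. Access during the trial is not excluded, but the documents do not suggest much uptake.

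**The data may exist elsewhere.** Some attachments in Protocol section 16 are unexplained acronyms, section 11b collects medical history, and VA records may be available. None of these is scheduled or tied to an analysis for this purpose.

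What stands is the conflict over who is in the trial, and the absence of any planned record or model term for programme status.

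**Conclusion.** The point holds as a cheap improvement and does not threaten validity. The current protocol is inconsistent about whether participants are in outpatient SUD treatment, and the plan neither schedules programme status for recording nor models it.

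With 25-75% of participants in the programme and an outcome difference of 0.25-0.8 SD, variance rises about 1-16% and power for d = .42 falls by under 7 points. A 1-in-20 chance imbalance would move a two-arm contrast by 0.04-0.15 SD, or up to about 0.19 SD if the difference were 1.0 SD. If d = .42 is meant on the total-SD scale, the power figures describe a gain forgone instead of a loss.

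The larger cost does not depend on these assumptions. Differences between arms in care taken up after randomisation would go undetected by the planned assessments, and readers could not tell whether the result applies to CBT-I as an adjunct to SUD treatment.

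**What to change.** 1. Reconcile Protocol sections 2a and 8c with sections 8g and 8h, so that the described population matches the one that can be enrolled.
2. At baseline, record whether the participant is enrolled in or scheduled for outpatient SUD treatment. Include this as a prespecified fixed effect in the H1.1, H1.2 and H2.1 models. Stratifying by it is optional: with small recruitment waves split into three groups, the covariate secures most of the benefit.
3. At existing assessments, record SUD therapy and non-study CBT-I received since the last visit, and report both descriptively by arm. Do not adjust the primary models for them: they arise after randomisation, may be affected by the assigned arm, and adjusting could itself introduce bias.

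The cost is one baseline item, two short follow-up items and one covariate, with no added visits or participants. It is best done early, because care received during follow-up is hard to reconstruct later, especially outside the VA.

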13.1 Consent consent form

Check if VA related Y

a) Describe the informed consent process. Include the following.

- i) Who is obtaining consent? (The person obtaining consent must be knowledgeable about the study.)**
- ii) When and where will consent be obtained?**
- iii) How much time will be devoted to consent discussion?**
- iv) Will these periods provide sufficient opportunity for the participant to consider whether or not to participate and sign the written consent?**
- v) What steps are you taking to minimize the possibility of coercion and undue influence?**
- vi) If consent relates to children and if you have a reason for only one parent signing, provide that rationale for IRB consideration.**

Consent will be obtained by the PI or her research staff. The study will be described to participants expressing interest and the participant will be scheduled to come to the Menlo Park division of the VA Palo Alto. During this visit, the study will be explained in depth and the study team member will go over all elements of the consent with the patient. The patient will be given a copy of the consent and given time to read it and ask questions. The study team member will ask the potential participants questions to insure that they understand the procedures and risks. We expect the consent process will generally take about 15 minutes, however, potential participants will be given as much time as they need to decide whether or not to participate. To minimize the possibility of coercion and undue influence, patients will be given as much time as they like to think about participating, will be allowed to take the consent forms home to think about their participation, and a study team member will discuss participation with them to make sure that they understand that participation will not alter their clinical care. No children will be participating in this study of veterans.

b) What is the Procedure to assess understanding of the information contained in the consent? How will the information be provided to participants if they do not understand English or if they have a hearing impairment? See /hrpp/Chapter12.html#ch12_2 HRPP Chapter12.2 for guidance.

The participant will be asked questions about the procedures and risks, and only when they can accurately describe them will they be able to consent. We are only recruiting veterans, and all veterans must understand English or they could not work in the military. Participants with a hearing impairment will be given the documents to read, and discussion of the consent will be conducted on a computer in the interview room where the study team member can type questions into a MS Word document and allow the potential participant to answer or type in questions of their own.

c) What steps are you taking to determine that potential participants are competent to participate in the decision-making process? If your study may enroll adults who are unable to consent, describe (i) how you will assess the capacity to consent, (ii) what provisions will be taken if the participant regains the capacity to consent, (iii) who will be used as a legally authorized representative, and (iv) what provisions will be made for the assent of the participant.

If potential participants cannot explain the study procedures and risks back to the study team member, they will be considered not competent to participate and not allowed to participate in the study.

Additional VA questions:

i) List the people to whom you have formally delegated responsibility to obtain informed consent, and state whether they have the appropriate training to perform this activity.

[name] or her research staff will have responsibility to obtain informed consent and have been trained in human subjects protection and the informed consent procedures.

ii) Will legally effective informed consent be obtained from the participant or the participant's legally authorized representative (LAR) or both? If LAR, is it clear who can serve as LAR?

Consent will be obtained from the participant alone.

iii) Will the circumstances of the consent process minimize the possibility of coercion or undue influence and provide the prospective participant or their representative sufficient opportunity to consider whether to participate?

The circumstances of the consent process should be minimally coercive and the participant will be given

Title: The Impact of CBT-I on Cannabis Cessation Outcomes
Approval Period: 03/27/2015 - 03/11/2016

time during the explanation to ask questions, will be provided the consent forms to look at for as long as they want, and will be given a phone number where they can reach study team members who can answer additional questions they may have. They can consider participating for as long as they like and are under no pressure to make an immediate decision.

iv) **Will the circumstances of the consent process minimize the possibility of coercion or undue influence?**

Yes, a witness to the participant's signature will sign and date the consent document and a copy of the signed and dated consent document will be given to the person signing the consent document.

v) **Will the information being communicated to the participant or the representative during the consent process exclude any exculpatory language through which the participant or the representative is made to waive or appear to waive the participant's legal rights, or release or appear to release the investigator, the sponsor, the institution, or its agent from liability for negligence (e.g. I give up any property rights I may have in bodily fluids or tissue samples obtained in the course of the research)?**

No.

vi) **Please confirm the following:**

- a. A witness to the participant's signature or the participant's legally authorized representative's signature will sign and date the consent document.
- b. If the sponsor or the IRB requires a witness to the consenting process in addition to the witness to the participant's signature and if the same person is needed to serve both capacities, a note to that effect is placed under the witness's signature line.
- c. A copy of the signed and dated consent document will be given to the person signing the consent document.
- d. The consent form is on the VA Form 10-1086.

